## 14.0 BIOSTATISTICS

This study will enroll thirty patients with advanced NSCLCs, who will receive nivolumab plus ipilimumab therapy following standard-of-care resection of tumor tissue. In order to be considered eligible for the primary and secondary objectives described in this study, patients must receive (1) at least one dose of study therapy and remain on study until at least the first radiographic tumor assessment (week 6) or (2) at least one dose of study therapy and have clear clinical or radiographic progression prior to the planned first radiographic tumor assessment at week 6. Patients who come off study for reasons other than clinical/radiographic progression prior to the first radiographic tumor assessment will be replaced.

The sample size is based on feasibility and budgetary considerations, as well as generating sufficient preliminary data to more specifically inform a larger study of sufficient power. In the thoracic surgery service, there is an average of 1-3 cases per week of patients with advanced stage disease who undergo intervention or resection of a metastatic site of disease and who may be eligible for this trial. We would expect that 20-40% of such patients would be willing to participate in this study and therefore anticipate an accrual rate of 1-2 patients per month, or 20 patients/year. We therefore expect to complete accrual in 18 months. Due to the limited sample size and to the heterogeneity of the patient population (both smokers and never smokers permitted, no restriction related to PD-L1 expression), we will not be able to draw definitive conclusions regarding the effect of specific factors and mechanisms. The nature of this study is descriptive and exploratory. Any hypotheses generated will need to be further confirmed. Response to nivolumab will be evaluated using RECIST criteria and patients will be classified as either responders (CR or PR at any time during nivolumab treatment) or non-responders.

Primary objective 1: In each tumor sample, we will quantify the mutational burden (number of somatic, non-synonymous mutations detected through whole exome sequencing) and investigate graphically its relationship with response to nivolumab plus ipilimumab. We will describe the burden of mutations for responders and non-responders using summary statistics, and compare it (in an exploratory analysis) using Wilcoxon rank sum test. Depending on the number of responses, we may also perform logistic regression with mutational burden as a covariate and/or use Cox regression to analyze PFS and OS with mutational burden as a covariate. We expect that higher burden of somatic mutations will show an indication of positive association with response to nivolumab plus ipilimumab. Patients will be stratified into mutation “high” and “low” groups based on the median number of non-synonymous mutations/sample in patients with NSCLCs, and we will report objective response rate along with exact 95% confidence intervals in the low and high burden groups, respectively. Because this is not an established categorization, we will graphically

investigate whether other types of functional relationship between the burden of mutation and response might be more appropriate.

#### Primary Objectives 2: Identification of candidate neoantigens

Candidate neoantigens will be broadly defined as those mutations that generate peptides that have <500nM binding affinity to patient specific MHC class I alleles. Analysis may be further refined by IEDB or in vitro methods to identify relevant neoantigens that are predicted to elicit T-cell response. Using these methods, a list of candidate neoantigens will be generated and we will use non-parametric Wilcoxon tests to compare responders vs non-responders with respect to the quantity of putative neoantigens. Those neoantigens significantly associated with response status (controlling for a false-discovery rate of 5%) will be validated in further studies. Data will be compared to TCGA data to see if there are mutated sequences enriched in either the responder or non-responder group.

#### Primary Objective 3: Identification of neoantigen-specific T-cells.

The presence of neoantigen-specific peripheral blood and (if possible) intratumoral T-cells will be quantified in pre- and on-treatment specimens. We will present these data graphically and summarize them for responders and non-responders. We are interested in observing whether neoantigen-specific T-cells exhibit patterns of change between the two evaluations that are different between responders and non-responders. The presence of neoantigen-specific lymphocytes will be quantified in samples collected at baseline and serially while on treatment. Their trajectory will be presented graphically, summarized separately for responders and non-responders, and compared using mixed-effects models for longitudinal data.

Secondary objectives: Tumor expression of co-stimulatory ligands and receptors and MHC expression will be analyzed and quantified in pre-treatment and on-treatment tissue samples. All measures, as well as percent changes between values pre- and during treatment, will be summarized separately for responders versus non-responders. Association between pre-treatment values and response will be explored using Wilcoxon rank sum test in order to investigate the predictive potential.

Exploratory analyses: Additional post-hoc, exploratory assessments are expected and may be performed. Much such as, but not limited to, logistic regression and graphical summaries may be used to assess associations between various potential biomarker measures and clinical efficacy.

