## **Secondary Objectives**

### 4) MHC and co-stimulatory receptor/ligand expression

The validity of tumor expression of PD-L1 as a predictive biomarker of response to anti-PD1 mAb is a topic of current debate. Tumors expressing PD-L1 contain tumor-infiltrating lymphocytes (TILs) that typically express PD-1 (37, 67, 94) but are dysfunctional (32, 95-98). These data support

the hypothesis that expression of PD-L1 on tumor cells or cells in the tumor microenvironment may be an adaptive mechanism of immune escape by binding to PD-1 on TILs and quieting a tumor-directed immune attack.

In this context, it is further hypothesized that PD-L1 expression is needed for response to anti-PD1 mAb, while tumors lacking PD-L1 are insensitive to anti-PD1 mAb and evade immune surveillance using alternate mechanisms (99). Currently available data suggest PD-L1 expression may enrich for response, but is neither necessary nor sufficient (24). We will integrate an evaluation of PD-L1 expression, MHC expression, as well as other co-stimulatory ligands, in patients treated with nivolumab plus ipilimumab using IHC, flow cytometry, or other methods if become available.

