\*Patients who experience initial progressive disease may continue therapy if they are experiencing clinical benefit. A CT scan should be repeated no earlier than 4 weeks after the first documentation of progressive disease. If there is more than 10% additional progression compared to baseline (e.g. first scan showed 24% growth relative to baseline, second scan shows 36% growth relative to baseline), then study therapy should be discontinued. If, instead, <10% further progression is seen, the patient may continue study therapy until confirmed progression of disease so long as there is continued clinical benefit (detailed in Section 9.0).

Protocol-related research blood draws will occur during screening, before treatment on C1D1 (+/- 1 day), C2D1 (+/- 3 days), C2D8 (+/- 1 day from date of on-treatment biopsy), C3D1 (+/-3 days), C4D1 (+/- 3 days), C5D1 (+/- 3 days), and at the end-of-study visit.

In addition to the baseline CT scan, which will occur after pre-treatment surgical resection or biopsy, tumor assessments will be performed with CT scans of the chest (+/- abdomen/pelvis depending on sites of known disease) every 6 weeks (+/- 1 week) while on treatment for up to 48 weeks. After 48 weeks, CT scans will be performed every 12 weeks (+/- 1 week). CT scans should occur every 6 (or 12) weeks throughout the patient's time on study irrespective of treatment interruptions or delays.

In addition to pre-treatment standard-of-care surgical resection or biopsy, a protocol-mandated tumor biopsy will be required at C2D8 (+/- 1 week) for all patients who remain on study at that time. The tumor biopsy should be optimally performed on a non-target lesion, if feasible.

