### Study Size

30 patients will be treated on this study. Patients who enroll on study but withdrawal study consent or for any other reason never receive study therapy will be considered a screen failure and will be replaced. Additionally, in order to be considered eligible for the primary and secondary objectives described in this study, patients must receive (1) at least one dose of study therapy and remain on study until at least the first radiographic tumor assessment (week 6) or (2) at least one dose of study therapy and have clear clinical or radiographic progression prior to the planned first radiographic tumor assessment at week 6. Patients who come off study for reasons other than clinical/radiographic progression prior to the first radiographic tumor assessment will be replaced.

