#### Co-stimulatory receptor and ligand expression:

FFPE tumor tissue collected from pre-treatment tumor resection and on-treatment biopsy will be examined for expression of PD-L1 on tumor and microenvironment cells by immunohistochemical (IHC) staining with the 28-8 antibody, and/or alternative method(s) if available. 3rd party vendors

have also developed IHC stains which may be used. In addition to PD-L1, there are other surface markers that may mediate immunogenicity and selective sensitivity to different immunotherapy approaches. These include, but are not limited to, MHC I, MHC II, PD-1, LAG-3, TIM-3 which can be examined by IHC, immunofluorescence, and/or flow cytometry.

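### Percent change is the only within-patient change measure named for on-treatment marker expression; read as relative change, it cannot show negative-to-positive shifts and is unstable at low baselines

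*Combined protocol and SAP*

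**What the plan says.** The secondary-objectives paragraph of Section 14.0, printed under the Primary Objective 3 heading, states that expression of co-stimulatory ligands, receptors and MHC "will be analyzed and quantified in pre-treatment and on-treatment tissue samples". It continues: "All measures, as well as percent changes between values pre- and during treatment, will be summarized separately for responders versus non-responders". The one test named for this objective is on baseline values: "Association between pre-treatment values and response will be explored using Wilcoxon rank sum test".

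Section 14.0 describes the population as having "no restriction related to PD-L1 expression". The rationale for this objective in Section 3.0 discusses the hypothesis that PD-L1 is needed for response, "while tumors lacking PD-L1 are insensitive to anti-PD1 mAb". Section 4.7 plans to examine "expression of PD-L1 on tumor and microenvironment cells by immunohistochemical (IHC) staining with the 28-8 antibody", or by alternative methods. It lists further markers (MHC I and II, PD-1, LAG-3, TIM-3) that may be read by IHC, immunofluorescence or flow cytometry.

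Section 4.7 gives no scoring scale or lower limit. Section 14.0 gives no offset, absolute or log change, or negative-to-positive category. It does not say whether percent change means relative change or a difference in percentage points.

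**The concern.** Relative change divides by the pre-treatment value. A tumor that scores zero at baseline has no defined value, whether it stays negative or becomes positive, so these two different courses both drop out and cannot be told apart. A tumor just above zero can produce a very large percentage from a small shift, and with few responders one or two such tumors can dominate a mean.

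The rationale in Section 3.0 treats PD-L1 expression as a possible adaptive route of immune escape. Expression that appears on treatment therefore bears on the protocol's own hypothesis, and a relative change cannot display it. Several markers are planned, so the difficulty can recur marker by marker. What is at stake is whether the paired change table, broken down by response, describes what happened in the tumors.

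**Working it through.** **Inputs.**
- Sample size: "30 patients will be treated on this study" (Study Size).
- Response rate: about 30% for the combination (Section 2.1), so 0.30 × 30 = 9 responders and 21 non-responders.
- On-treatment tissue: "a protocol-mandated tumor biopsy will be required at C2D8 (+/- 1 week) for all patients who remain on study at that time" (Section 4.3).
- Share f of tumors scoring zero on a given marker: not in the documents. Assumed range 20-50%; a wider 10-60% is also shown.

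The plan states no figure for this analysis, and the sample size rests on feasibility and budget, so there is nothing to reproduce.

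**Step 1: behaviour of the measure.** Percent change = 100 × (on − pre) / pre. For the same rise of 5 units:

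| Baseline | On treatment | Absolute change | Percent change |
|---|---|---|---|
| 0 | 5 | +5 | undefined |
| 0.5 | 5.5 | +5 | +1000% |
| 1 | 6 | +5 | +500% |
| 5 | 10 | +5 | +100% |
| 50 | 55 | +5 | +10% |

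**Step 2: patients without a value.** Expected number = f × 30, if all 30 have paired, evaluable tissue. Expected responders remaining = 9 × (1 − f), if f is the same in both response groups.

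| Assumed f | No percent change, of 30 | Responders remaining, of 9 |
|---|---|---|
| 10% | 3 | 8.1 |
| 20% | 6 | 7.2 |
| 30% | 9 | 6.3 |
| 40% | 12 | 5.4 |
| 50% | 15 | 4.5 |
| 60% | 18 | 3.6 |

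With m < 30 paired patients the loss caused by the measure is f × m. Patients without a second biopsy have no change value on any scale.

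**Step 3: two constructed examples (illustrations, not trial data).**
- *Instability.* Nine tumors with baselines 0, 0, 0, 1, 1, 5, 20, 50 and 80 all rise by 5 units. Three are undefined. The other six give 500, 500, 100, 25, 10 and 6.25%: mean 1141.25 / 6 = +190%, median (100 + 25) / 2 = +62.5%. The absolute change is +5 in every tumor. A median tempers the extremes but does not bring back the three lost tumors.
- *Missed induction.* Three zero-baseline tumors rise to 20 and six positive tumors do not change. Mean absolute change is 3 × 20 / 9 = +6.7. Mean percent change in the six computable tumors is 0%.

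**Step 4: what is untouched.** A tumor going from 0 to 20 still contributes 0 to the pre-treatment summary and 20 to the on-treatment summary. In the Wilcoxon test on pre-treatment values, zeros stay in as ties.

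**The case against.** The strongest reply is that the same sentence also summarizes the measures themselves, so marker-negative patients are not lost from the on-treatment description. That stands, and it confines the point to the change summary. It does not remove it: separate group summaries at two time points do not show paired change, and they may cover different patients, because the second biopsy is taken only from those still on study.

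A second reply is that no test is planned on percent change and that Section 14.0 calls the study descriptive and exploratory. That also stands. A reader might infer that the responder versus non-responder comparison as a whole is biased; the documents do not support this, since the only named test uses baseline values.

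Third, percent change could mean percentage points on a percent-positive scale, in which case a zero baseline causes no difficulty. The text does not settle this. Nor does it say that undefined cases will be dropped; it is silent, and the allowance for further exploratory analyses permits a repair without specifying one.

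Fourth, a reader might infer that induction from zero is the change that matters most to this protocol. Section 3.0 makes it relevant but does not rank it, and the stated objective is the relation of expression with response.

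Finally, percent change need not be deleted. Absolute change has floor and ceiling limits (a tumor at 95% positive cannot rise 20 points), and intensity or flow readouts may be better read on a relative scale. That is a sound reason to add measures rather than replace one.

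**Conclusion.** The point holds for the paired change summary of the secondary markers, provided that percent change means relative change and that some tumors score at or near zero. The enrolment rule and the rationale make zero baselines foreseeable. Followed as written, the summary cannot display negative-to-positive shifts and overweights low-baseline tumors.

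The size is not known from the documents: 6-15 of 30 patients without a value follows only from the assumed 20-50% share and complete pairing, and is smaller with fewer pairs. The summaries of values and the Wilcoxon test are unaffected. Severity is low, because this is one descriptive summary in an exploratory secondary objective, but the improvement is cheap.

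**What to change.** In the secondary-objectives paragraph of Section 14.0:

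1. State the scoring scale for each marker and what counts as negative, and say whether percent change is relative or in percentage points.
2. In patients with paired tissue, report absolute change in the marker's own units, with median and range, by response.
3. Add a table of baseline negative/positive against on-treatment negative/positive, by response.
4. Keep percent change only as a supplement, and give the number of patients in each response group in whom it is undefined.

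This needs a few lines of text and a little more tabulation, with no new patients, tissue or assays. The floor and ceiling limits of absolute change remain; the shift table and the retained percent change partly offset them.

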## **15.1 RESEARCH PARTICIPANT REGISTRATION AND RANDOMIZATION PROCEDURES**

### **15.2 Research Participant Registration**

Confirm eligibility as defined in the section entitled Inclusion/Exclusion Criteria. Obtain informed consent, by following procedures defined in section entitled Informed Consent Procedures.

During the registration process registering individuals will be required to complete a protocol specific Eligibility Checklist. The individual signing the Eligibility Checklist is confirming whether or not the participant is eligible to enroll in the study. Study staff are responsible for

ensuring that all institutional requirements necessary to enroll a participant to the study have been completed. See related Clinical Research Policy and Procedure #401 (Protocol Participant Registration).

### **15.3 Randomization**

N/A

## **16.1 DATA MANAGEMENT ISSUES**

A Research Study Assistant (RSA) will be assigned to the study. The responsibilities of the RSA include project compliance, data collection, abstraction and entry, data reporting, regulatory monitoring, problem resolution and prioritization, and coordinate the activities of the protocol study team. The data collected for this study will be entered into a secure database (Clinical Research Database (CRDB)). Source documentation will be available to support the computerized patient record. The principal investigator will maintain ultimate responsibility for the clinical trial.

### **16.2 Quality Assurance**

Weekly registration reports will be generated to monitor patient accruals and completeness of registration data. Routine data quality reports will be generated to assess missing data and inconsistencies. Accrual rates and extent and accuracy of evaluations and follow-up will be monitored periodically throughout the study period and potential problems will be brought to the attention of the study team for discussion and action. Random-sample data quality and protocol compliance audits will be conducted by the study team, at a minimum of two times per year, or more frequently if indicated.

### **16.3 Data and Safety Monitoring**

The Data and Safety Monitoring (DSM) Plans at Memorial Sloan-Kettering Cancer Center were approved by the National Cancer Institute in September 2001. The plans address the new policies set forth by the NCI in the document entitled "Policy of the National Cancer Institute for Data and Safety Monitoring of Clinical Trials" which can be found at:

[http://www.cancer.gov/clinicaltrials/patientsafety/dsm\\_guidelines/page1](http://www.cancer.gov/clinicaltrials/patientsafety/dsm_guidelines/page1)

The DSM Plans at MSKCC were established and are monitored by the Clinical Research Administration. The MSKCC Data and Safety Monitoring Plans can be found on the MSKCC Intranet at:

[http://smskpsps9/dept/ocr/OCR%20Website%20Documents/Clinical%20Research%20Quality%20Assurance%20\(CRQA\)/MSKCC%20Data%20and%20Safety%20Monitoring%20Plan.pdf](http://smskpsps9/dept/ocr/OCR%20Website%20Documents/Clinical%20Research%20Quality%20Assurance%20(CRQA)/MSKCC%20Data%20and%20Safety%20Monitoring%20Plan.pdf)

There are several different mechanisms by which clinical trials are monitored for data safety and quality. There are institutional processes in place for quality assurance (e.g., protocol monitoring, compliance and data verification audits, therapeutic response, and staff education on clinical research QA) and departmental procedures for quality control, plus there are two institutional committees that are responsible for monitoring the activities of our clinical trials programs. The

committees: Data and Safety Monitoring Committee (DSMC) for Phase I and II clinical trials, and the Data and Safety Monitoring Board (DSMB) for Phase III clinical trials, report to the Center's Research Council and Institutional Review Board.

During the protocol development and review process, each protocol will be assessed for its level or risk and degree of monitoring required. Every type of protocol (e.g., NIH sponsored, in-house sponsored, industry sponsored, NCI cooperative group, etc.) will be addressed and the monitoring procedures will be established at the time of protocol activation.

## 17.1 PROTECTION OF HUMAN SUBJECTS

Prior to the enrollment of each patient, the risks, benefits and objectives of the study will be reviewed with the participant, including a discussion of the possible toxicities and side effects. Alternative, non-protocol, treatment options will be discussed with the patient. It will be reviewed that participation in this clinical trial is voluntary and that the patient may withdraw consent at any time. The study is designed with careful safety monitoring for toxicity including physician visits. Specific guidelines for symptom management are in place to protect the study participant.

Human Subjects Involvement and Characteristics: All patients at MSKCC who meet the all of the inclusion and none of the exclusion criteria will be eligible. At least 30 patients will be enrolled. Patients eligible will be 18 years of age or older with a ECOG performance status  $\leq 1$ . Both men and women and members of all ethnic groups are eligible for this trial. Pregnant and breast-feeding women are excluded from this study. This protocol does not include children because the number of children is expected to be limited for the patient population expected to be accrued onto this study. Also, the majority of children are already accessed by a nationwide pediatric cancer research network. This statement is based on exclusion 4b of the NIH Policy and Guidelines on the Inclusion of Children as Participants in Research Involving Human Subjects.

Consent process: All patients at MSKCC who meet the inclusion criteria will be eligible. Participation in the trial is voluntary. All patients will be required to sign a statement of informed consent, which must conform to IRB guidelines. The informed consent procedure is described in Section 18.0.

Possible Toxicities/Side-Effects: There are risks associated with treatment as described in Section 11.0; however, patients screened for enrollment will be deemed appropriate for treatment independent of this study.

Benefits: Based on data from a Phase I trial, nivolumab plus ipilimumab appears to benefit some patients with lung cancers. At present, it is unknown what the predictors of that response are. The goal of this study is to evaluate the potential somatic genetic predictors of objective response to nivolumab plus ipilimumab in patients with lung cancer.

Costs: Patients will be charged for physician visits, routine laboratory tests, and radiologic studies required for monitoring their condition. Pre-treatment tumor resections will be performed as standard-of-care.

The cost of research-only biopsies, nivolumab, as well as tumor tissue based- and blood based-exploratory correlatives will be covered by research funds.

Alternatives: For patients considering this trial as second-line therapy, docetaxel or erlotinib could be alternative standard options. Nivolumab would also be a standard option for patients with squamous cell lung cancer. For patients considering this trial as third-line therapy or beyond, there are no standard treatment alternatives.

Confidentiality: Every effort will be made to maintain patient confidentiality. Research and hospital records are confidential. Patients' names and any other identifying information will not be used in reports or publications resulting from this study. Other authorized agencies and appropriate internal personnel (e.g. qualified monitors from MSKCC) and external personnel (e.g. qualified monitors from BMS (the manufacturer of nivolumab and ipilimumab), its authorized agents, the FDA, and/or other governmental agencies) may review patient records as required.

Future Contact: Participants will not be routinely told of the results from research assays (e.g. DNA sequencing). With their permission, the participant and/or family members may be contacted in the future to ask if they are interested in learning about potential findings of inherited risks for cancer that may have been an outcome of the research assay testing of their samples.

Patient safety: Patients are monitored by physicians and oncology nurses who are very familiar with clinical trials. In the case of an adverse reaction, immediate medical attention is available. In the evenings and weekends, we have a 24-hour urgent care facility for outpatients. The PI or co-PI will also be available at all times to organize any necessary intervention.

Monitoring of data to ensure safety: This study is to be monitored by the institutional IRB. This incorporates an independent data and safety monitoring board established by arrangement with the National Cancer Institute. The analysis of safety will include all patients. Adverse events, including all toxic effects of treatment, will be tabulated individually, and summarized by severity and causality.

